5.1.2.9 Administration of Study Treatment

Variables related to administration of treatment will be summarized for safety population by treatment group as follows.

Table 5-12 Exposure to Study Treatment

Endpoint	Description	Timing	Methodology
Pretreatment	Separately for each of cannula	Treatment	Categorical
anesthesia type	and needle cheeks. Also,		Counts.
and duration	combined across cannula and		For injection
 Planes of 	needle for anesthesia type and		ease: responder
injection	number of injections.		descriptives with
• Injection			paired-
technique			comparison
Needle/cannula			difference and CI
used			
 Number of 			
injections			
Injection ease			

5.1.3 Effectiveness Analyses

Effectiveness analyses will be based on the mITT Population.

The following effectiveness assessments are defined:

Table 5-13 Effectiveness Assessments

Assessment	Description
Cheek severity by MFVDS	Assessed by EI based on 6-point MFVDS (see Appendix A).
FACE-Q Satisfaction with Cheeks	Assessed by subjects based on 4-point FACE-Q for 5 items (see Appendix B).

Baseline assessments for applicable effectiveness endpoints defined as follows:

Table 5-14 Effectiveness Endpoint Baseline Definitions

Endpoint	Description	Timing			
Cheek severity by MFVDS	Baseline refers to the last evaluation prior to treatment	Screening Day -30			
FACE-Q Rasch Score	Baseline refers to the last evaluation prior to treatment	Screening Day -30			

5.1.3.1 Primary Effectiveness Analysis

For the primary effectiveness analysis of change from baseline at Month 1 in EI-assessed overall MFVDS, the mean paired difference between treatment with cannula and treatment with needle,

and its 95% CI based on the paired t-test will be calculated. If the upper confidence limit is less than 0.5, statistical non-inferiority will be concluded.

[figure not shown]

Table 5-15 Primary Effectiveness Analyses

Endpoint	Description	Timing	Methodology		
MFVDS change from	Compare mean difference in the	Baseline and change	Continuous		
baseline to month 1	MFVDS change from baseline score	from baseline to	descriptives with		
	between cannula and needle at Month	months 1	paired-comparison		
	1,		CI		

5.1.3.2 Secondary Effectiveness Analysis

The following analyses will be performed for secondary effectiveness variables:

• FACE-Q Satisfaction with Cheeks module (subject self-assessment) change from baseline at Month 1 Visit will be summarized with descriptive statistics. For secondary effectiveness, this will be done for the Rasch transformed score. The 5 component item scores will be summarized under other effectiveness analysis.

[figure not shown]
To control the overall type I error rate at 5%, treatment comparison for the secondary MFVDS responder variable will not be deemed significant unless the comparison for the primary effectiveness variable is statistically significant. No significance testing of FACE-Q will be done.

[figure not shown]
Table 5-16 Secondary Effectiveness Analyses

Endpoint	Description	Timing	Methodology
Responder rate based on	non-inferiority of cannula to needle	Responder	
MFVDS change from	with respect to responder rates at 1		descriptives with
baseline scores of ≥ 1	month, with tertiary support at month 3		paired-comparison
			difference and CI
FACE-Q Rasch scores	subject level (rather than by treatment)	Baseline and change	Continuous
	response distribution, for Rasch	from baseline to	descriptives
	transformed scores on 0-100 scale	months 1	

The sum of the FACE-Q 5-item scores for a subject's visit will be set to missing if more than 2 items have missing scores. If only 1 or 2 items have missing scores, the sum score will be calculated by prorating (ie, by 5/4 or 5/3, respectively) the sum of the non-missing scores and rounding the result to the nearest integer. (This is essentially imputation by mean substitution.) Following is a conversion look-up table for mapping the sum of the FACE-Q 5-item scores to its Rasch transformed score.

Sum Score	5	6	7	8	9	10	11	12	13	14	15	16	17	18	19	20
Rasch Score	0	13	20	25	30	35	40	44	50	55	63	70	77	83	91	100

5.1.4 Safety Analyses

Safety analyses will be based on the Safety Population.

Baseline assessments for applicable safety endpoints defined as follows:

Table 5-18 Safety Endpoint Baseline Definitions

Endpoint	Description	Timing
 Vital signs 	eCRF- or (standardized) vendor-provided	Latest non-missing
	assessments	assessment
		on/before treatment
		start date

5.1.4.1 Study Treatment Exposure and Compliance

See Section 5.1.2.8.

5.1.4.2 Adverse Events

The following AE terms are defined:

Table 5-19 AE Terms

Term	Description
Treatment-	An AE that initially occurs or increases in severity on or after the treatment start date.
emergent AE	
(TEAE)	
Treatment-	A TEAE that is related to study treatment in the judgment of the investigator.
related TEAE	
(TR-TEAE)	

AEs, encompassing abnormalities and surgeries reported as occurring after the Screening Visit, will be coded using MedDRA version 20.0 or newer. A listing of all TEAEs will be presented. Also, unique subjects reporting AEs as well as number of events in the following AE categories will be summarized by treatment group and in total for the Safety Population as follows (ie, AEs at cheeks, AEs not at cheeks and all AEs combined). The overall summary tables of AE categories and the summary tables for TEAEs and TR-TEAEs that are grouped by SOC, PT and severity will be included within a CSR-appendix set of tables. The other AE summary tables listed will be generated within a supplemental set of tables.

Table 5-20 AE Summaries

Endpoint	Description	Timing	Methodology
Overall summary	Overall summary only for the following categories:	Treatment	Categorical counts
	 Treatment-emergent AEs (TEAEs) Treatment-related TEAEs All Serious AEs (SAE) 		
	Treatment-related SAE		
	Discontinued due to TEAEDeaths		
TEAEs	 by SOC and PT by SOC, PT, and severity (mild, moderate, severe) by SOC, PT, and duration (≤ 7 days, 8-14 days, 15-30 days, > 30 days) non-serious and occur ≥ 5%, by SOC and PT 	Treatment	Categorical counts
TR-TEAEs	by SOC and PTby SOC, PT, and severity	Treatment	Categorical counts
SAEs ¹	Overall summary and by PT	Treatment	Listing
AEs leading to discontinuation ¹	Overall summary and by PT	Treatment	Listing

¹ Subjects who report ≥ 1 AE in the AE category and all AEs for those subjects will be listed. SOCs will be sorted alphabetically; PTs will be sorted in descending frequency across treatments (cannula and needle).

5.1.4.3 Injection Site Responses

ISRs recorded in subject diaries after treatment will be summarized by pre-defined symptoms.

Table 5-21 ISR Analyses

Endpoint	Description	Timing	Methodology
ISR incidence	Incidence of occurrence. Response	30 days post	Categorical counts
	distribution for cannula, needle, cannula	treatment	
	only, needle only.		
ISR severity	Maximum reported severity. Response	30 days post	Categorical counts
	distribution for cannula, needle, cannula	treatment	
	only, needle only.		
Number of ISR days	Number of days with ISR reported during	30 days post	Categorical counts
	the 30-day diary period. Response	treatment	
	distribution for cannula, needle, cannula		
	only, needle only.		
ISR total duration	Total duration from first instance of the	30 days post	Categorical counts
	ISR to the last instance of the ISR within	treatment	
	the treatment period, where last instances		
	means no further report to the end of the		
	30-day diary period. Response distribution		
	for cannula, needle, cannula only, needle		
	only.		

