7.2 Safety Measures

Safety measures will include:

- subject assessment of procedural pain during treatment on an 11-point scale [REDACTED]
- presence and severity (mild, moderate, or severe) of ISRs recorded by subjects in daily safety diaries for 30 days after treatment
- AEs observed by the TI or reported to the TI by the subject

The subject's daily safety diary will list the following ISRs that have been reported previously with HA dermal filler injections:

- redness
- pain after injection
- tenderness to touch
- firmness
- swelling
- lumps/bumps
- bruising
- itching
- discoloration

AEs will be monitored continuously throughout the study and documented on an AE eCRF.

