7.5 Summary of Methods of Data Collection

Electronic data capture and questionnaires will be used to collect study-specific information, such as subject and Investigator assessments. Completed eCRFs will be reviewed by the Investigator, and the designated monitor will verify the data. Investigators will provide access to hospital files, medical records, and other source documents containing subject clinical/medical information. Source document verification will be performed.

8. Statistical Procedures

A separate statistical analysis plan will be prepared to provide specifications for all analyses. The plan will be finalized and approved prior to clinical database lock.

Descriptive statistics will be presented for key outcome measures. Categorical variables will be summarized with response frequencies and percentages. Continuous variables will be summarized by number of subjects, mean, median, standard deviation, minimum, and maximum. Where appropriate, 2-sided 95% CIs for population mean, or population proportion, will be provided as part of the summary.

Every attempt will be made to collect complete data and limit the occurrence of missing data. No imputation of missing data is planned, except for sensitivity analyses described in Section 8.3.1 and to account for days with missing reports during the ISR duration discussed in Section 8.3.4.

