8.3.4 Safety Analyses

ISRs, procedural pain assessment, and AEs will be summarized using descriptive statistics. The primary safety analysis of ISRs and AEs will be summarized by the percentage (and 95% CI) of subjects who have the ISR (or AE) on both sides, by the percentage (and 95% CI) of subjects who have the ISR (or AE) on the cannula side and not on the needle side, and by the percentage (and 95% CI) of subjects who have the ISR (or AE) on the needle side and not on the cannula side. Also, the within-treatment percentage (and 95% CI) of subjects who have the ISR (or AE) will be summarized for the cannula side and, separately, for the needle side.

ISRs reported by subjects will be summarized by symptom, maximum reported severity, maximum reported duration (ie, calendar days from first occurrence to last reported occurrence during the 30-day ISR period), and number of ISR days (ie, calendar days with non-zero severity, after accounting for days with missing reports during the ISR duration). Adverse events will be summarized by System Organ Class and Preferred Term, and will be tabulated by duration, severity, causality, action taken, relationship to treatment, and outcome. The summary will include incidence rate as well as total number of events. AEs that occur before treatment will be listed, but not summarized.

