4.2 Study Objectives and Endpoints

The objective of this study is to evaluate the safety and effectiveness of VOLUMA XC injectable gel using cannula in subjects seeking correction of age-related volume deficit in the mid-face.

The study primary objective, secondary objective, and other objectives are presented with corresponding endpoint(s) below:

Table 4-1 Study Objectives and Corresponding Endpoints

Objectives	Endpoints	
To evaluate the safety and effectiveness of cannula versus needle for the correction of age-related volume deficit in the mid-face.	Primary Endpoint: • MFVDS response distribution by treatment, based on EI assessment on a 6-point scale of ordinal categories, from 0 to 5 (none, minimal, mild, moderate, significant, severe), for baseline and change from baseline to month 1 (primary endpoint)	
	 MFVDS responder rates by treatment, based on EI assessments on a 6-point scale of ordinal categories, from 0-5 (none, minimal, mild, moderate, significant, severe), with responders defined as ≥1 grade improvement from baseline, for month 1 (primary measurement time) Subject's FACE-Q Satisfaction with Cheeks, at the subject level rather than by treatment (because the questions are asked regarding the face rather than the treatment sides), for the 	

FACE-Q Rasch transformed score (0-100), which is converted from the sum score (range 5-20) across 5 items (symmetric, smooth, attractive, contour, and fullness), with each item scored on an ordinal scale from 1 to 4 (very dissatisfied, dissatisfied, satisfied, very satisfied); the FACE-Q Rasch score will be summarized for baseline and change from baseline to month 1 (primary measurement time)

[figure not shown]
Safety Assessments

- AEs, separately for AEs at cheeks, not at cheeks and combined
- Procedural Pain, based on subject assessment on an 11-point scale,
 response distribution by treatment, and paired treatment comparison

of each subject's difference score (-10 to +10)

• Injection Site Responses (ISR), based on subject's 30-day diary, overall and for each of 10 categories (redness, pain after injection, tenderness to touch, firmness, swelling, lumps/bumps, bruising, itching, discoloration and other), response distribution by treatment, separately for presence, severity (none, mild, moderate, severe), number of ISR days (none, 1-3, 4-7, 8-14 and 15 or more), and total duration (none, 1-3, 4-7, 8-14 and 15 or more days)

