5.1.1.4 Missing Data

If there are any mITT subjects with missing scores for the primary effectiveness endpoint, the following 2 missing-data handling methods are pre-specified to use for missing-data sensitivity analysis of the primary effectiveness endpoint. For each method, there will be no missing baseline MFVDS, because protocol inclusion criteria 2 requires a score of 3, 4 or 5.

Table 5-3 Missing Data Handling by Endpoint Type

Endpoint type	Timing	Missing Data Handling
Categorical Response	Month 1	 All subjects included (mITT population) Multiple imputation (eg, via SAS procedure MI) within treatment, with 5 imputed datasets, will be applied to subjects with missing post-baseline MFVDS scores, using the following model: Month 1 MFVDS = β₀+β₁ Baseline MFVDS + β₂ Month 3 MFVDS
Categorical Response	Month 1	 All subject included (mITT population) Baseline observation carried forward (BOCF) for subjects
1		with missing post-baseline MFVDS values.

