5.3 Changes in the Conduct of the Study or Planned Analyses

The PP definition in the study protocol was enhanced (see Table 5-1) to specifically exclude subjects who did not receive each assigned treatment on its assigned side for this paired-comparison study. The intent is that such cases would be identified as significant protocol deviations, but, in case they are not, the enhanced definition specifically excludes them from the PP population. Also, the study populations defined in the protocol were expanded (see Table 5-1) to include the screened population and the ITT population, because those definitions are needed for some of the data listings.

6. Data Handling and Analysis Conventions

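### SAP Table 5-21 counts only reported ISR days and omits, without declaring it, the protocol's correction for missing diary days

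*SAP*

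**What the plan says.** Protocol Section 7.2 has ISR presence and severity "recorded by subjects in daily safety diaries for 30 days after treatment". Protocol Section 8.3.4 lists among the ISR summaries the "number of ISR days (ie, calendar days with non-zero severity, after accounting for days with missing reports during the ISR duration". Protocol Section 8 (Statistical Procedures) rules out imputation apart from the sensitivity analyses of the primary endpoint and a second exception, "to account for days with missing reports during the ISR duration discussed in Section 8.3.4". It leaves detailed specifications to the SAP and gives no algorithm for the correction.

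SAP Table 5-21 describes the same outcome as "Number of days with ISR reported during" the 30-day diary, summarised by categorical counts. Table 4-1 gives the bands: "number of ISR days (none, 1-3, 4-7, 8-14 and 15 or more". Table 5-21 has no rule for a missed diary day. SAP Section 5.1.1.4 is confined to the primary endpoint ("If there are any mITT subjects with missing scores for the primary effectiveness endpoint"), and Section 6.3 deals with partial dates. SAP Section 5.3, on changes from the protocol, covers the per-protocol definition ("The PP definition in the study protocol was enhanced (see Table 5-1") and two added populations. It says nothing about ISRs.

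**The concern.** The two documents state different rules for one outcome. The protocol's rule was deliberate, since it is carved out as an exception to a general ban on imputation. A programmer working from Table 5-21 would count reported days only, so a gap inside an episode would add nothing to the count, as if the cheek had been clear that day. A programmer working from the protocol would have to invent a method, possibly after seeing the data.

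At stake is how long each technique's local reactions appear to last. Symptom days would be understated on both sides. Because the table reports bands, one lost day can move a subject into a lower category. The table also shows total duration next to ISR days. Under a raw count, missed entries would make the two rows diverge and look like intermittent symptoms.

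**Working it through.** The documents give no missed-diary rate and no expected ISR days, so there is no stated figure to reproduce. What follows is illustrative.

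**Inputs.** The bands come from SAP Table 4-1: none, 1-3, 4-7, 8-14, 15 or more. Assumptions: the ISR is continuous for D days, and each diary day is missed independently with probability m = 5%, 10% or 20%. The correction is modelled as span × (non-zero days ÷ reported days in the span), where the span runs from first to last reported occurrence. For a continuous ISR this equals filling the interior gaps.

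**1. Mean count.** Expected reported days = D(1 − m). For D = 8 this gives 7.60, 7.20 and 6.40 at m = 5%, 10% and 20%, an undercount of 5%, 10% and 20%. With interior gaps filled, the simulated means are 7.89, 7.78 and 7.50. The small remaining loss comes from missed first or last days.

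**2. Falling below a band.** At a band's lower bound (D = 4, 8, 15), any missed day moves the subject down under the raw count, with probability 1 − (1 − m)^D. After the correction, only a missed first or last day does so, with probability 1 − (1 − m)². At m = 10% the latter is 1 − 0.9² = 19%.

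| D (days) | Raw count, m = 10% | After correction | Recoverable |
|---|---|---|---|
| 4 | 1 − 0.9⁴ = 34% | 19% | about 15 points |
| 8 | 1 − 0.9⁸ = 57% | 19% | about 38 points |
| 15 | 1 − 0.9¹⁵ = 79% | 19% | about 60 points |

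At m = 5% the raw figures are 19%, 34% and 54%, against 1 − 0.95² = 10% after correction.

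These are worst cases. Away from the lower bound, by the binomial tail at m = 10%, the raw count drops a 5-day ISR one band in 8% of subjects, a 6-day ISR in 2% and a 10-day ISR in 7%.

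**3. Cannula-needle comparison.** With equal m on both sides, the difference in mean days shrinks by the factor (1 − m). For 5 against 8 days, a true difference of 3 becomes 2.85, 2.70 and 2.40; the ratio stays at 5/8. In the SAP's bands there is no fixed direction. At m = 10%:

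| True days, shorter vs longer side | Cut | True gap (points) | Gap under raw count |
|---|---|---|---|
| 5 vs 10 | 8 or more | 100 | 93 |
| 5 vs 10 | 4 or more | 0 | about 8 |
| 7 vs 8 | 8 or more | 100 | 43 |
| 8 vs 10 | 8 or more | 0 | about 50 |

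Letting durations vary between subjects (simulated negative binomial, means 7 and 9, m = 20%) also gives a mixed result. The gap at 4 or more days goes from 8.5 to 9.8 points, at 8 or more from 12.1 to 11.7, and at 15 or more from 8.4 to 5.8.

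**The case against.** Table 5-21 is a short description, and its silence on missed days need not displace the protocol's fuller definition, which the SAP says it elaborates. Parts of the SAP cannot be read, including Table 5-2 and Section 5.1.5, so a derivation rule could sit there. This caveat stands. However, the defining row and Section 5.3 are both readable, and neither carries the correction.

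The practical weight is also limited. Protocol Section 8.3.4 plans that "ISRs, procedural pain assessment, and AEs will be summarized using descriptive statistics", and its primary ISR analysis is the percentage of subjects affected on both sides or on one side only. No test or paired interval for ISR days is readable. Total duration, from first to last instance, is kept and is not shortened by interior gaps. The treating investigator reviews the diary with the subject at Month 1 (SAP Section 4.1.1), which may reduce missing entries. All of this stands and limits the consequence.

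A reader might go further and infer that the raw count makes the two techniques look alike. The documents do not support that. The narrowing holds for the absolute difference in mean days under equal missingness, a summary the readable SAP does not plan for ISR days. In the planned bands the gap can narrow or widen. If missing entries differed by side, the direction would be unknown.

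**Conclusion.** The point holds as an undeclared conflict between protocol and SAP on how ISR days are counted. Followed literally, the SAP understates mean ISR days by about the missed-day fraction and moves subjects near a band boundary downward. Any gain from the correction depends on an assumed missing rate, a continuous ISR and independently missed days. At 10% missed, the recoverable misclassification is at most about 15, 38 and 60 points for ISRs of exactly 4, 8 and 15 days, and nothing if diaries are complete. The full 34%, 57% and 79% should not be attributed to the omission, because 19% would still drop a band after the correction. No claim about the direction of the cannula-needle comparison is warranted, and no inferential result changes. The protocol's exception to its own imputation rule should still be either implemented or openly withdrawn.

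**What to change.** Before database lock, put the protocol definition into Table 5-21 with an explicit rule for missing days between the first and last reported occurrence. One option is ISR days = span in days × (non-zero days ÷ days with a diary report in the span), rounded to a whole day before banding. The protocol names no algorithm, so another stated rule would also serve. State how missing days before the first and after the last report are treated. Keep the raw count as a supportive row and report missing diary days per subject. If the raw count is what the sponsor intends, list it in SAP Section 5.3 with a reason.

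The cost is a sentence or two in the SAP and a small programming change. The rule assumes that missing days inside the span resemble reported ones, and it does not recover missed first or last days.

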4.1.1 Overall Design

This is a prospective, multicenter, evaluator-blind, randomized, within-subject, controlled, paired-comparison study of the safety and effectiveness of VOLUMA XC injectable gel using a cannula versus needle for cheek augmentation to correct age-related volume deficit in the midface.

Subjects eligible for study enrollment should have cheeks that are either moderate for both cheeks, significant for both cheeks or severe for both cheeks, as assessed by the EI using the 6-point photonumeric Mid-Face Volume Deficit Scale (MFVDS), ranging from 0-5 (0 = none, 1 = minimal, 2 = mild, 3 = moderate, 4 = significant, 5 = severe).

Eligible subjects will be randomized to undergo treatment with cannula in the right or left cheek and with needle in the other cheek (ie, treatment groups will be "cannula left and needle right" or "needle left and cannula right). Prior to randomization, the subjects' demographic information and cosmetic, medical, surgical and dental history will be recorded. Physical measurements and vital signs will be collected, and a urine pregnancy test will be conducted for women of childbearing potential.

The Treating Investigator (TI) and subject will not be blinded to treatment assignment. The Evaluating Investigator (EI) is to remain blinded to treatment assignments for each cheek throughout the duration of the study. Hence, this is considered to be a single-blind study, although some measurement variables are unblinded (eg, injection ease rated by the treating investigator and procedural pain rated by the subject).

diary for 30 days after the treatment session beginning on the day of treatment. Subjects will

return 1 month after treatment, and the TI will evaluate the treatment areas for localized reaction and will review the safety diary with the subject and discuss reported symptoms.

Subjects will attend follow-up visits for safety and effectiveness at Months 1 and 3 after treatment. Safety and effectiveness assessments will be performed at posttreatment follow-up visits. The EI will rate subjects on the MFVDS for each cheek, the TI (or designee other than EI) will record any adverse events (AEs), and subjects will complete the Satisfaction with Cheeks module of the FACE-Q questionnaire. At the month 3 visit, a urine pregnancy test will be performed for female subjects of childbearing potential. Subjects will be exited from the study at the Month 3 visit after study procedures are completed.

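### The ISR duration rule has no provision for a diary that stops while the response is still present, so a cut-off duration is tabulated unmarked among completed ones

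*SAP*

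**What the plan says.** Subjects keep the diary for 30 days, counted from the treatment day (SAP 4.1.1: "diary for 30 days after the treatment session beginning on the day of treatment").

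SAP 5.1.4.3, Table 5-21, defines the endpoint as "Total duration from first instance of the" ISR to its last instance, and explains that the last instance "means no further report to the end of the" 30-day diary period. Protocol 8.3.4 gives the same quantity as "maximum reported duration (ie, calendar days from first occurrence to last reported occurrence during the 30-day ISR period".

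The results are tabulated as categorical counts. SAP Table 4-1 lists the classes: "total duration (none, 1-3, 4-7, 8-14 and 15 or more days".

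The only allowance for missing diary days is in the protocol. The opening of Section 8 permits imputation "to account for days with missing reports during the ISR duration discussed in Section 8.3.4". Section 8.3.4 applies it to the number of ISR days: "calendar days with non-zero severity, after accounting for days with missing reports during the ISR duration".

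**The concern.** The last report can be the last for two reasons: the ISR went away, or the subject stopped filling in the diary. The rule treats both alike. The missing-day allowance does not help, because it works inside the ISR duration, and the duration by definition ends at the last report. Blank days after that point are never reached.

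A subject with bruising from Day 1 who makes the last entry on Day 6 is counted in the 4-7 day class, next to subjects whose bruising cleared on Day 6. The table does not show which is which.

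Safety of cannula use is part of the study objective, and duration is one of four ISR outputs in Table 5-21. A stopped diary shortens the recorded time on both cheeks from the same day. Durations are understated for both devices, and the cannula and needle distributions look more alike than they are.

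**Working it through.** The plan states no figure tied to this rule, so there is nothing to reproduce. The check applies the rule day by day and then sizes the effect under stated assumptions.

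**Step 1. The rule.** Recorded duration = last reported day − first reported day + 1. The documents do not say whether the count is inclusive; without the +1, every cut-point below moves by one day.

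**Step 2. Diary stops early.** Take an ISR that starts on Day 1 and truly lasts to Day 30.

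| Last diary entry | Class recorded | Correct class |
|---|---|---|
| Day 1-3 | 1-3 | 15 or more |
| Day 4-7 | 4-7 | 15 or more |
| Day 8-14 | 8-14 | 15 or more |
| Day 15 or later | 15 or more | 15 or more |

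Any stop before Day 15 puts this ISR in too short a class.

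**Step 3. Diary complete, ISR present on Day 30.** Recorded duration = 30 − onset day + 1.

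| Onset | Recorded duration | Class |
|---|---|---|
| Day 1-16 | 30 to 15 days | 15 or more, correct however long it continues |
| Day 17-23 | 14 to 8 days | 8-14, possibly too low |
| Day 24-27 | 7 to 4 days | 4-7, possibly too low |
| Day 28-30 | 3 to 1 days | 1-3, possibly too low |

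Misclassification at the end of the diary needs onset on Day 17 or later.

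**Step 4. Size.** The documents give neither diary completion nor ISR persistence. Assumptions: onset on Day 1; lognormal durations with median 11 days (needle) and 8 days (cannula), log-SD 0.8, rounded up to whole days; a share *d* of subjects stops the diary, unrelated to ISR length, with the last entry uniform on Days 2 to 29.

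- True share at 15 days or more = 1 − Φ(ln(14/median)/0.8). Needle: ln(14/11)/0.8 = 0.301, giving 38.15%. Cannula: ln(14/8)/0.8 = 0.700, giving 24.21%.
- A long ISR is misclassed if the last entry is on Days 2-14, which is 13 of the 28 possible days.
- Recorded share = true share × (1 − *d* × 13/28). The factor is 0.977 at *d* = 5% and 0.907 at *d* = 20%.

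| Diaries stopped | Needle, 15 or more | Cannula, 15 or more | Gap between sides |
|---|---|---|---|
| None | 38.15% | 24.21% | 13.94 points |
| 5% | 37.27% | 23.65% | 13.62 points |
| 20% | 34.61% | 21.96% | 12.65 points |

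A simulation under the same assumptions gives 38.1%, 37.2% and 34.6% for the needle. If the 20% all stop between Days 2 and 15, the fraction becomes 13/14 and the needle share is 38.15 × (1 − 0.2 × 13/14) = 31.1%.

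**Step 5. Scale.** With 60 treated subjects, a fall from 38.1% to 34.6% is 0.035 × 60, or about 2 subjects. The standard error of such a percentage is √(0.381 × 0.619/60) = 6.3 points.

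**The case against.** A reader might infer that these ISRs are reported as resolved. The documents do not support that. Table 5-21 tabulates no resolution status, only a "Response distribution" over duration classes, and the protocol openly labels the quantity as the reported duration within 30 days. The defect is a cut-off duration without a mark.

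A reader might also infer that ISRs present on Day 30 are generally miscounted. They are not. The top class is open-ended and is correct for any onset by Day 16. For those ISRs the table only fails to show how many were still ongoing.

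A third inference would be that the rule biases a planned cannula-needle comparison of duration. No mean, test or paired contrast for duration appears in the readable text, and the primary non-inferiority analysis does not use these data. The drawing together of the two sides is a matter of how the descriptive tables read.

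The effect may be small. At 5% stopping it is about one percentage point. Even at 20% over Days 2-29 it is roughly half a standard error.

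Finally, diary instructions and visit procedures are largely redacted, and SAP 4.1.1 has the treating investigator examine the treatment areas and review the diary at Month 1. A rule for incomplete diaries may exist in text that cannot be seen. The readable duration rule does not use that review, however.

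These points limit the scope and size. None supplies a rule for blank days after the last report.

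**Conclusion.** The point holds for diaries that stop early. As written, the SAP and protocol place an ISR still present at a last entry before about Day 15 in too short a class, unmarked, on whichever cheeks are affected. For a complete diary, misclassification is confined to onset on Day 17 or later; otherwise what is missing is a count of ongoing ISRs.

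The direction is clear: durations are understated and the two sides are drawn together. The size is not known. The fall in the needle share from about 38% to between 37% and 35% rests on assumed durations and on 5% to 20% of subjects stopping on Days 2-29; earlier stopping would make it larger. The scope is descriptive safety reporting. The change is worth making because it is cheap and because the SAP already does better for adverse events: Section 6.3 leaves the stop date of an ongoing event missing, and Table 5-20 separates durations of 15-30 days from longer ones.

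**What to change.** In Table 5-21, and in the matching derivation:

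- Treat an ISR as ended only if at least one later completed diary day shows it absent.
- Otherwise flag it as *ongoing at last diary entry* and report its duration as a minimum.
- Add a row, by cannula and needle side, counting the flagged ISRs, with those present on Day 30 shown separately from those whose diary stopped earlier.

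Do not add a paired duration contrast restricted to resolved ISRs or complete diaries. It looks like a natural companion but keeps early stoppers only when their ISRs were short, so it selects on the outcome. Under the assumptions above, with a between-side correlation of 0.6 and 20% stopping on Days 2-29, it gives a mean difference of 2.87 days, against a true 3.01 and 2.72 under the SAP rule. Nor should the fix rely on ISR status at Month 1, since no readable field shows that it is recorded.

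The cost is one derivation flag, one or two extra rows per ISR table, and slightly less favourable durations. It uses diary data already collected.
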